Day (days) ^c	-28 to -1	1	3(±1)	8(±2)	15(±2)	22(±2)	24(±1)	29(±2)	36(±2)	43(±2)	57(±3)	71(±4)	85(±3)	99(±4)
Plasma complement levels (C3a and C5a) ⁿ		X							X					
MGFA classification	X	X								X				X
QMG scale	X	X		X	X	X		X	X	X		X		X
MG-C scale	X	X		X	X	X		X	X	X		X		X
MG-ADL	X	X		X	X	X		X	X	X	X	X	X	X
MG Symptoms PRO	X	X		X	X			X		X		X		X
PGI-S	X	X			X			X				X		X
PGI-C					X			X				X		X
EQ-5D-5L		X								X				
MGII ^o		X								X				
MG-QOL15r		X								X				
Study drug discontinuation criteria				X	X	X		X	X					
Study withdrawal criteria	X	X	X	X	X	X	X	X	X	X	X	X	X	X

AChR=acetylcholine receptor; ADA=anti-drug antibody; AE=adverse event; AESM=adverse events of special monitoring; BL=Baseline; C-SSRS=Columbia Suicide Severity Rating Scale; ECG=electrocardiogram; EQ-5D-5L=EuroQol-5D-5L; EOS=End of Study; EOT=End of Treatment; GI=gastrointestinal; HIV=human immunodeficiency virus; IgA=immunoglobulin A; IgE=immunoglobulin E; IgG=immunoglobulin G; IgM= immunoglobulin M; IGRA=interferon-gamma release assay; IMP=investigational medicinal product; INR=international normalized ratio; IRT=interactive response technology; MG=myasthenia gravis; MG-ADL=myasthenia gravis-Activities of Daily Living; MG-C=Myasthenia Gravis Composite; MGFA=Myasthenia Gravis Foundation of America; MGII=Myasthenia Gravis Impairment Index; MG-QOL15r=Myasthenia Gravis Quality of Life; MuSK=muscle-specific kinase; PEOT=premature end of treatment; PGI-C=Patient Global Impression of Change; PGI-S=Patient Global Impression of Severity; PK=pharmacokinetics; PTT=partial thromboplastin time; PRO=patient-reported outcome; QMG=Quantitative Myasthenia Gravis; TB=tuberculosis; V=Visit

^a This visit can be scheduled as a home visit, unless the study participant prefers to attend the site.

^b This visit will be a virtual visit, unless the study participant prefers to attend the site.

- ^c A visit window of ± 1 day is allowed for V3 and V7. A visit window of ± 2 day is allowed for all dosing visits. The visit window of ± 2 days is relative to the first dosing visit date. However, there should be a minimum interval of 5 days and maximum interval of 9 days as compared to the previous dose. A visit window of ± 3 days is allowed for V11 and V13. A visit window of ± 4 days is allowed for V12 and V14.
- ^d Refer to Section 1.4.
- ^e Only weight will be repeated at Baseline (V2).

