4.4 End of Study definition

A study participant is considered to have completed the study if he/she has completed all phases of the study including the Observation Period. Study participants will have an EOS Visit performed 8 weeks after the last dose of study medication, or upon discontinuation of the study. The EOS is defined as the date of the last visit of the last study participant in the study.

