8.3.8 Treatment-emergent adverse events

Treatment-emergent AEs are defined as AEs starting after the time of first IMP administration up to and including 8 weeks after the final dose.

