9.5 Planned Safety and other Analyses

9.5.1 Safety analyses

The frequency and severity of all TEAEs will be presented for each treatment group separately by System Organ Class, high level term, and preferred term (Medical Dictionary for Regulatory Activities [MedDRA][®]). The data will be displayed as number of study participants experiencing the TEAE, percentage of study participants, and number of TEAEs. A TEAE is defined as any event that was not present prior to the first administration of IMP or any unresolved event already present before the first administration of IMP that worsens in intensity following exposure to treatment.

Laboratory evaluations and vital signs as well as ECG data will be analyzed over time. All safety analyses will be listed and summarized for the SS.

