10.2 Adverse events

10.2.1 Data considerations

Adverse events will be recorded from the time of informed consent until study completion. All AEs will be coded ([Section 3.8](#)).

In addition, AEs will be classified according to the Common Terminology Criteria for Adverse Events (CTCAE) Version 5 or later for severity. For any AEs where it is not possible to provide a CTCAE grading, the events will be assessed using a standard intensity classification (mild,

moderate and severe). For the purpose of the tabulations all CTCAE severity classifications will be mapped to a mild/moderate/severe grade as described below:

- Grade 1-- Mild
- Grade 2-- Moderate
- Grade 3, 4, 5-- Severe

These will be tabulated together with the AEs that were not classified according to CTCAE criteria i.e., all Grade 1 AEs as per CTCAE criteria will be included in the 'mild' category together with those AEs classified as mild as per the 'standard' intensity classification. In the case a mapped standard intensity classification per above rule is different from the standard intensity classification on CRF, the worst case will be used as the standard intensity classification (i.e. an AE with Grade 1 and moderate as intensity classification will be classified into moderate).

A TEAE is defined as an AE starting on or after the time of first administration of IMP up to and including 8 weeks (56 days) after the final dose. Adverse events starting before the date of the first administration of IMP or after 8 weeks following the final dose of IMP will not be considered TEAEs. Thus AEs before first dosing and AEs after 8 weeks following the final dose will be combined in one category. Such events will be listed only.

Where dates are missing or partially missing, AEs will be assumed to be treatment-emergent unless evidence exists that does not allow the AE to be treatment-emergent. Handling of missing dates for classification of AEs as TEAEs is described in [Section 4.2.2](#).

The following rules will be used to assign a TEAE to a study period:

- **Treatment Period:** a TEAE will be assigned to the Treatment Period for the tabulations if the start date of the event is on or after the date of the first administration of IMP on Day 1, up to 7 days following the final dose of IMP

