Note: Treatment-emergent is defined as meeting the criteria at any post-Baseline visit after the first infusion of study medication and within 56-days of the last infusion and not meeting the same criteria during Baseline

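### The 56-day treatment-emergent window closes about a week before the scheduled EOS visit, so AEs starting in that last week, and PR/QRS abnormalities first seen at EOS, are collected but not counted as treatment-emergent

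*SAP*

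**What the plan says.** **Window.** SAP 10.2.1 closes the TEAE window "up to and including 8 weeks (56 days) after the final dose". Protocol 8.3.8 has the same limit, "up to and including 8 weeks after the final dose". Under SAP 10.2.1, AEs that start later are grouped with pre-dose AEs and appear in listings only. The same section assigns a TEAE to the Observation Period if it starts more than 7 days and no more than 8 weeks after the final dose.

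**A second definition.** Protocol 9.5.1 sets no upper time limit: "A TEAE is defined as any event that was not present prior to the first administration of IMP", or a pre-existing event that worsens. SAP 3.9, which lists departures from the protocol, does not mention the difference.

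**Timing.** The Schedule of Activities puts the sixth and last dose at Visit 9, Day 36±2, and EOS at Visit 14, Day 99±4. Its footnotes state "The visit window of ± 2 days is relative to the first dosing visit date", require a "minimum interval of 5 days and maximum interval of 9 days as compared to the previous dose", and add "A visit window of ± 4 days is allowed for V12 and V14". Protocol 4.4, by contrast, describes an "EOS Visit performed 8 weeks after the last dose of study medication".

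**Collection.** Protocol 8.3.1 collects all AEs from consent to the EOS visit.

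**ECG.** In SAP 13.7 the PR (>200 ms) and QRS (>100 ms) criteria apply to treatment-emergent values. A note defines these as arising after the first infusion and "within 56-days of the last infusion and not meeting the same criteria during Baseline". The QT, QTcF and heart-rate criteria carry no such condition.

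**The concern.** The analysis window and the visit schedule count eight weeks from different starting points. The window runs from the last dose. The scheduled Observation Period runs from Visit 10, one week later. The last week of planned safety follow-up therefore lies outside the window.

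Occurrence of TEAEs is a secondary safety endpoint, and the incidence tables in SAP 10.2.2 are built on TEAEs. Visit 14 is the only on-site safety visit scheduled after Visit 12, since Visit 13 is virtual by default and has no laboratory tests, ECG or examination. Visit 14 also has the only scheduled ECG after Visit 10. Protocol 7.1.2, 8.2.1 and 8.2.4 require clinically relevant ECG, examination and laboratory findings to be recorded as AEs. A finding first seen and dated at Visit 14 is thus collected as an AE but missing from the incidence tables.

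**Working it through.** **Inputs.** Window: 8 weeks (SAP 10.2.1, Protocol 8.3.8). Last dose: Day 36±2; Visit 10: Day 43±2; Visit 13: Day 85±3; EOS: Day 99±4 (Schedule of Activities).

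**1. The plan's own figures.**
- 8 × 7 = 56 days, as the SAP states.
- Observation Period counted from Visit 10: 43 + 56 = Day 99, which matches the Schedule.
- EOS counted from the last dose, as in Protocol 4.4: 36 + 56 = Day 92, which does not match the Schedule.

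**2. Nominal gap.**
- Window closes: 36 + 56 = Day 92.
- EOS after last dose: 99 − 36 = 63 days.
- Days outside the window: 99 − 92 = 7 (Days 93 to 99).
- Share of follow-up after the last dose: 7/63 = 11%.

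**3. Permitted visit windows.** Enumerating every dosing sequence within ±2 days and with 5- to 9-day intervals leaves the last dose anywhere on Days 34 to 38. EOS can fall on Days 95 to 103.
- Shortest gap: 95 − 38 = 57 days.
- Longest gap: 103 − 34 = 69 days.
- Excess over 56: 1 to 13 days. No permitted combination brings EOS inside the window.
- Visit 13: 82 − 38 = 44 to 88 − 34 = 54 days, always inside.

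**4. Observation Period coverage.** The period runs from Day 44 to Day 99, which is 56 days. SAP 10.2.1 tabulates Observation Period TEAEs from Day 44 (36 + 7 = 43, so from the next day) to Day 92, which is 49 days. That is 49/56, or 7 of 8 weeks.

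**5. Early stopping, as an illustration.** Protocol 4.1 has rescue users stop IMP, complete the remaining visits through Visit 10, and then enter the Observation Period. Assume the last dose is on Day 8 and follow-up runs to Day 99:
- Window closes: 8 + 56 = Day 64.
- Outside: 99 − 64 = 35 of 99 − 8 = 91 days, or 38%.

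If instead a premature end-of-treatment visit near Day 15 starts an 8-week Observation Period, that period ends near 15 + 56 = Day 71. This is 71 − 8 = 63 days after the last dose, so 7 days fall outside, as for a completer.

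**6. Which outputs the window governs.**
- TEAE incidence tables (SAP 10.2.2): affected.
- PR and QRS markedly abnormal counts (SAP 13.7): affected at Visit 14.
- QT, QTcF and heart-rate markedly abnormal counts, by-visit ECG summaries, and the shift to worst post-Baseline ECG (SAP 10.4.2): not affected.
- Laboratory and vital-sign markedly abnormal counts at any visit, laboratory shift tables, and liver-injury criteria (SAP 10.3, 10.3.1, 10.4.1): not affected.
- Late AEs in listings, and the all-deaths row of the overview table: not affected.

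**The case against.** The strongest defence is that the window was prespecified. SAP 10.2.1 implements Protocol 8.3.8 exactly, and some cut-off after the last dose is ordinary practice. Eight weeks also has some support: Protocol 4.2 reports that in the first-in-human study total IgG was generally back to Baseline by Day 57 on average. But that was a single-dose study, and neither document offers it as the reason for the TEAE window. The same section sets the 8-week Observation Period to follow IgG and autoantibody recovery and the durability of effect. For rescue users, late AEs also follow IVIg or PEX, so some cut-off can be argued for. None of this explains collecting a week of AEs that the tables omit, or why Protocol 9.5.1 has no cut-off.

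Other limits stand. A reader might infer that everything found at the final visit is lost, or that ECG changes there never count. The documents do not support that:
- Most abnormality tables take any visit, and only PR and QRS carry the condition.
- Physical examination and C-SSRS results are listed only, whatever the window.
- AEs are classified by onset, so one reported at Visit 14 that began by Day 92 is a TEAE.
- Missing or partial onset dates default to treatment-emergent unless the evidence rules it out.
- Participants who complete EOS early to enter the extension study may fall inside the window.

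Nor is 38% a general figure for early stoppers; it needs a Day 8 last dose and follow-up to Day 99. No bias between arms is shown. Counted follow-up would differ by arm only if early stopping did.

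**Conclusion.** The concern holds in a limited form. For participants who receive the last dose at Visit 9 and attend Visit 14 within its window, AEs with known onset after the 56 days (nominally Days 93 to 99, or 11% of follow-up after the last dose) are left out of all TEAE incidence tables. So are PR and QRS abnormalities first seen at Visit 14. More follow-up falls outside for participants who stop IMP early but are followed to Day 99.

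The conclusion rests on the Schedule's visit days. If EOS took place 8 weeks after the last dose, as Protocol 4.4 says, it would nominally fall on Day 92, the last day inside the window. The two statements of EOS timing must therefore be reconciled, as must the two protocol definitions of a TEAE. The expected effect on incidence is small. The change is still worth making because it aligns a secondary safety endpoint with the follow-up the trial collects.

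**What to change.** - In SAP 10.2.1, end the treatment-emergent window at the later of 56 days after the last dose and the participant's EOS visit or last contact in this study. Extend the Observation Period assignment rule to match.
- Apply the same end to the SAP 13.7 ECG note, where it governs PR and QRS.
- Make the matching change in Protocol 8.3.8 and reconcile it with the open-ended definition in Protocol 9.5.1. If the protocol is not amended, record the departure in SAP 3.9.
- Reconcile Protocol 4.4 with the Schedule of Activities on when EOS occurs. The proposed window works under either timing.
- Keep the 56-day version as a supportive table, for comparison with any other study that uses that window.

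The cost is SAP and protocol wording and a rerun of the AE tables and the PR/QRS counts. Reported incidence would rise slightly in all arms.

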- **Observation Period:** a TEAE will be assigned to the Observation Period for the tabulations if the start date of the event is greater than 7 days after the date of the final dose of IMP until 8 weeks following the final dose; events starting later than 8 weeks following the final dose of IMP are not considered TEAEs

In the case of early withdrawal in the Treatment Period, a TEAE will be assigned to the Treatment Period based on the last received IMP plus 168 hours (7 days). Subsequent TEAEs (up to 8 weeks post-last dose) will be assigned to the Observation Period.

A TEAE will be counted as a TEAE related to IMP if the response to the question "Relationship to Study Medication" is "Related". Severe TEAEs are those with CTCAE Grade 3 or above, or those without a CTCAE grading classified as 'severe' by the Investigator.

Es will be presented as "number of study participants (percentage of study participants) [number of events]". In this style of output, "[number of events]" will include all cases of an AE including repeat occurrences in individual study participants, while "number of study participants" will count each study participant only once.

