10.2.2 AE summaries

Summary tables with the number, percentage of study participants and frequency of TEAEs will be provided by treatment group and RLZ total. Additional details are as follows:

1. Overview of TEAEs will include following categories: any TEAEs, serious TEAEs, participant discontinuation due to TEAEs, permanent withdrawal of IMP due to TEAEs, temporary withdrawal of IMP due to TEAEs, treatment-related TEAEs, severe TEAEs, TEAEs leading to death, all deaths (AEs leading to death).
2. Incidence of TEAEs will be summarized by SOC, HLT and PT for:
 - Any TEAEs
 - TEAEs during Treatment Period
 - Severe TEAEs
 - Any TEAEs by maximum intensity (mild, moderate and severe)
 - Any TEAEs by relationship
 - Any TEAEs relative to ADA status
 - Any TEAE by Risk Difference $\geq 5\%$ (by decreasing frequency of Risk Difference)
 - Non-serious TEAEs above reporting threshold of 5% of study participants
 - Fatal TEAEs
 - Fatal TEAEs by relationship
 - Serious TEAEs
 - Serious TEAEs by relationship
 - Participant discontinuation due to TEAEs
 - TEAEs leading to permanent withdrawal of IMP
 - TEAEs leading to temporary withdrawal of IMP
 - Treatment-emergent AESM
 - Treatment-emergent AESI
3. Incidence of TEAEs will be summarized by PT for:
 - Any TEAEs by decreasing frequency of PT

AESMs include severe headache, severe GI disorders (i.e., abdominal pain, diarrhea, vomiting), and opportunistic infection.

AESIs are the cases of potential Hy's Law (see [Section 10.3.1](#)).

AESMs and AESIs will be identified based on the assessment by the Investigator as recorded in the CRF. An AE will be counted as an AESM if there is a 'yes' response to the question "Adverse event of Special Monitoring?" and 'no' otherwise. An AE will be counted as an AESI

if there is a ‘yes’ response to the question “Adverse Event of Special Interest?” and ‘no’ otherwise.

When applicable adverse event summaries will be ordered by alphabetical SOC, alphabetical HLT within SOC and decreasing frequency of PT in the rozanolixizumab total column for tables.

Listings of all TEAEs, all non-serious TEAEs, serious TEAEs, permanent withdrawal of IMP due to AEs, study participant discontinuation from study due to AEs, AEs leading to death, AESIs, AESMs will be presented by treatment group and study participants.

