10.2.3 Adverse Events of Focus

Rozanolixizumab treatment-emergent adverse events of Focus (TEAEof) include the following categories:

- Headaches
- Gastrointestinal disturbances
- Hypersensitivity reactions
- Anaphylactic reactions
- Injection site reaction
- Infusion reaction
- Opportunistic infections
- Reductions in albumin and plasma proteins
- Effects on the kidney
- Drug related hepatic disorders

A by-subject listing of all treatment-emergent AEOF by category (as listed above) will be provided. The number and percentage of study participants who experience each treatment-emergent AEOF will be summarized by most recent dose level prior to onset of AEOFs and total Rozimab treatment group. The following summaries will be presented by SOC, HLT, and PT:

- Treatment-emergent AEOF
- Serious Treatment-emergent AEOFs
- Treatment-emergent AEOFs by relationship
- Treatment-emergent AEOFs by maximum intensity (mild, moderate and severe)
- Treatment-emergent AEOF hypersensitivity reactions, anaphylactic reactions and infusion reactions by ADA
- Treatment-emergent AEOF headache and GI disturbances in Treatment period by intensity
- Treatment-emergent AEOFs by Risk Difference (by decreasing frequency of Risk Difference)

Graphs for treatment-emergent AEOF headache by time of onset (relative to infusion), severity, causality and duration for each study participant will also be provided.

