10.2.4 Safety analysis by weight subgroup and administered dose

To support the goal of a fixed dosing strategy for Rozanolixizumab, additional summary tables with the number, percentage of study participants and frequency of TEAEs (when applicable) will be provided by weight subgroup and administered dose and by SOC, HLT and PT for:

- Overview of TEAEs
- Incidence of TEAEs
- Incidence of Serious TEAEs
- Incidence of Severe TEAEs
- Incidence of AEOF of headache and GI disturbances
- Incidence of AEOF of headache and GI disturbances by maximum intensity (mild, moderate and severe)

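### SAP 10.2.1 gives two rules for a severe TEAE, and they disagree when an event has CTCAE Grade 1 or 2 but is rated severe on the CRF

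*SAP*

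**What the plan says.** SAP 10.2.1 (Data considerations) deals with adverse event intensity twice.

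- **Rule A, mapping with a worst-case step.** "For the purpose of the tabulations all CTCAE severity classifications will be mapped to a mild/moderate/severe grade": Grade 1 is mild, Grade 2 moderate, Grades 3 to 5 severe. If the mapped category differs from the intensity on the CRF, "the worst case will be used as the standard intensity classification". The example given is that "an AE with Grade 1 and moderate as intensity classification will be classified into moderate".
- **Rule B, the definition of the term.** "Severe TEAEs are those with CTCAE Grade 3 or above, or those without a CTCAE grading classified as" severe by the Investigator.

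Both feed planned outputs. The overview table in SAP 10.2.2 has the rows "treatment-related TEAEs, severe TEAEs, TEAEs leading to death". The same section plans a severe TEAE incidence table and a table of all TEAEs by maximum intensity. SAP 11.1 repeats this set for participants in Japan. SAP 10.2.4 plans "Incidence of Severe TEAEs" by weight subgroup and administered dose, but limits maximum-intensity tables there to headache and GI disturbances.

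Protocol 10.3.3 (Assessment of Intensity) treats CTCAE as a supporting tool and requires the Investigator's final rating to be mild, moderate or severe.

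**The concern.** Rule A lets a CRF rating raise a graded event. Rule B lets the Investigator's rating count only when there is no grade. An event graded 1 or 2 and rated severe on the CRF therefore gets two answers, and the SAP does not say which prevails.

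Such events are plausible. Protocol 10.3.3 allows both ratings on one event, and the scales have different anchors. Severe in Protocol 10.3.3 means the participant cannot carry on usual daily activities. The CTCAE-based definition of severe headache in Protocol Appendix 23 requires pain that restricts self-care, such as bathing or dressing. An event can meet the first standard without meeting the second. The worst-case sentence would itself be unnecessary if discordant ratings were not expected.

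At stake is the severe TEAE count in the safety report. In the main and Japan sets a mismatch would be visible, because a maximum-intensity table for all TEAEs stands beside the severe TEAE table. In the weight and administered-dose set, an affected event other than headache or GI disturbance would be shown as severe in no table of that set. Those tables are meant to support the fixed-dosing strategy.

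**Working it through.** The plan states no figure to reproduce, so the check is to apply both rules to every possible pair of ratings.

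**Inputs** (SAP 10.2.1): CTCAE state is none or 1 to 5 (6 states); CRF intensity is mild, moderate or severe (3 states). 6 × 3 = 18 pairs.

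- Rule A: severe if the worse of (mapped grade, CRF intensity) is severe. With no grade, the CRF intensity stands.
- Rule B: severe if the grade is 3 or more, or if there is no grade and the CRF intensity is severe.

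| CTCAE grade | CRF intensity | Rule A | Rule B |
|---|---|---|---|
| None | mild, moderate | not severe | not severe |
| None | severe | severe | severe |
| 1 | mild, moderate | not severe | not severe |
| **1** | **severe** | **severe** | **not severe** |
| 2 | mild, moderate | not severe | not severe |
| **2** | **severe** | **severe** | **not severe** |
| 3, 4, 5 | any | severe | severe |

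**Counts.**

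- Rule A: 1 (no grade) + 1 (Grade 1) + 1 (Grade 2) + 9 (Grades 3 to 5) = 12.
- Rule B: 1 + 9 = 10.
- Severe under A only: 2. Severe under B only: 0.
- Allowing a missing CRF intensity adds five pairs (Grades 1 to 5 with none), and the rules agree on all five. That gives agreement in 21 of 23 combinations, with the same two conflicts.
- If severe is defined as the Rule A result, there are 0 conflicts in 23.

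**Weight of one affected participant** (arm sizes from SAP 2.4, assuming everyone counted is dosed):

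- Stage 1 arm only: 1/30 = 3.3 percentage points.
- Arm continuing through Stage 2, 60 to 80 in total: 1/60 = 1.7 to 1/80 = 1.3 points.
- One dose continuing, if the 240 cap were applied: 30 + 150/2 = 105, so 1/105 = about 1.0 point.
- Rozanolixizumab total with both doses continuing, 120 to 160: 1/120 = 0.8 to 1/160 = 0.6 points.

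A dropped arm may exceed 30, because enrolment continues during the interim analysis (SAP 4.4.1). The sizes of the weight and Japan strata are not given, so no figure is offered for them.

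**The case against.** The best counter-argument is that Rule B is shorthand for Rule A. The mapping is said to cover all CTCAE classifications for tabulation, and Rule B's two limbs (graded, not graded) follow the section's opening, which reserves the standard scale for events that cannot be graded. This does not hold. Limiting the Investigator's rating to ungraded events matters only for graded events, which are exactly those the worst-case step covers. Rule B also makes no reference to a final or mapped intensity.

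A second argument is that each output already has its own rule and can be programmed, so the problem is only that two tables may not reconcile. That is feasible, but the same report would then use severe in two senses without saying so.

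Three points do stand.

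- Protocol 10.3.3 bears on the case of two ratings, so the worst-case rule is the only SAP rule for it but not the only text. For the two disputed pairs the protocol also points to severe, which supports the fix.
- SAP 10.2.3 plans maximum-intensity tables for all AEs of focus, summarised by most recent dose level. This narrows the gap by dose, though not by weight. Every affected event still appears as severe in the main maximum-intensity table, and all TEAEs are listed.
- The 1/n percentages apply to any single misclassified participant. They scale the problem; they do not measure how often it occurs.

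**Conclusion.** The concern holds. SAP 10.2.1 contains two definitions that differ for Grade 1 and Grade 2 events rated severe on the CRF. The literal definition of a severe TEAE can only give an equal or lower count. The conflict covers 2 of 18 rating pairs. The number of events is unknown and may be zero, since it depends on how often sites record both ratings and how often these disagree.

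The effect is confined to descriptive safety outputs: the overview row and the severe TEAE tables in the main, Japan and weight/administered-dose sets. Efficacy analyses and stopping decisions are unaffected. AESM counts come from a CRF question and are also unaffected. The matter should be corrected because the error runs in one direction, towards understating severity, and the correction is trivial.

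**What to change.** Replace the Rule B sentence in SAP 10.2.1 with a definition that a severe TEAE is one whose final intensity is severe after the CTCAE mapping and the worst-case step. State that this single variable is used for the overview row and all severe TEAE tables in SAP 10.2.2, 10.2.4 and 11.1.

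Using the Investigator's rating alone would also settle the two disputed pairs. However, it would downgrade six pairs (Grades 3, 4 or 5 with CRF mild or moderate) that both SAP rules now call severe. Adopting the worst-case rule changes only the two pairs in dispute.

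The cost is one sentence and no new data. Severe TEAE counts may rise slightly.
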